**Determining the Efficacy and Value of Immunotherapy on the
likelihood of peanut tolerance: The DEVIL Study**

Statistical Analysis Plan

NCT number NCT00932828

Document Date 04/08/2013

Sample size

No placebo-controlled studies have been published that evaluated the development of tolerance/SU after years of treatment with peanut OIT. Published data from our own uncontrolled pilot study in older children with long-standing disease suggest that SU developed in 12 of 24 (50%) peanut-allergic subjects completing high-dose OIT. (Vickery, et al. Sustained unresponsiveness to peanut in subjects who have completed peanut oral immunotherapy. *J Allergy Clin Immunol*. 2014 Feb;133(2):468-75. doi: 10.1016/j.jaci.2013.11.007). On the basis of preliminary data that were available to us at the time this study was conceived in 2008, and according to our hypothesis, we predicted before the study that 70% of low-dose subjects would develop SU, compared with the expected rate of spontaneous peanut allergy resolution of 20% as shown in multiple cohort studies. At a 2-sided significance level of .05, 15 subjects in each treatment arm would have at least 80% power to detect a 50% absolute average difference between the proportion of subjects in each arm passing the exit SU OFC and the 20% rate of spontaneous tolerance expected in untreated controls. On the basis of a prestudy assumption of 15% to 20% dropout, we enrolled 20 subjects per arm to ensure adequate power.

Practical considerations prevented a trial large enough to show definitive comparisons of high- and low-dose therapy directly. Twenty subjects in each arm would have 63% power to identify a 40% difference in SU acquisition between regimens. Even if underpowered to show a difference between low-dose and high-dose therapy, we reasoned a priori that a type II error in this setting may still be clinically meaningful so long as the proportion achieving SU in the low-dose group significantly exceeded 20%. This would be especially true if low-dose therapy offers other advantages (fewer visits, better safety profile, improved palatability, etc).

Randomization

For the primary outcome analysis, subjects were considered a single intervention group on open label peanut OIT. For exploratory analyses, subjects were randomized 1:1 to be on either low dose OIT (300mg peanut protein) or high dose (3000mg peanut protein). Masking was achieved by the addition of oat flour to the low dose OIT in order to match the weight of the high dose OIT product. Patients, patient families, study coordinators and investigators were blinded to the dose allocation. Randomization was conducted by unblinded laboratory staff in the [name] lab using a block randomization scheme.

Statistical Analysis

We computed averages, variances, frequencies, proportions, and graphical displays for all variables and examined them to ensure parametric distributional assumptions were met. Nonparametric test statistics were used as appropriate. Baseline demographics and categorical peanut consumption outcomes were compared between E-OIT and controls using Fisher's exact test. Analyses were performed with GraphPad Prism 6 for Mac (La Jolla, CA) or Stata/SE 13.1 (College Station, TX). To achieve approximate normality and variance stabilization for longitudinal immune analyses, pslgE and pslgG4 were log-transformed, while for SPT raw data were employed. Models were fit separately for each group in R (www.r-project.org) for each outcome with functions of time using generalized estimating equations. Linear and quadratic,

and cubic models in time were considered, with the best fitting model selected for each group for each outcome selected using QIC. All hypothesis tests were two-sided, with $p < 0.05$ considered significant.

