The present research plan draws upon our extensive knowledge of the allergens involved in peanut hypersensitivity; it is also based upon evidence demonstrating the effectiveness of peanut oral immunotherapy (OIT) in preliminary research studies. Previous attempts to utilize peanut-specific immunotherapy (IT) subcutaneously have failed primarily because of the side effects of therapy. We expect PMIT to have fewer side effects than the non-mucosal systemic desensitization method, and this proposal will compare a high dose regimen to a low dose regimen, which may improve the safety profile of PMIT. We propose to test the efficacy of PMIT in young peanut-allergic subjects; we believe that early intervention with PMIT, prior to the development of sustained immunologic memory, may offer an optimal treatment for affected subjects.

Our **hypothesis** is that mucosal peanut immunotherapy will make subjects who have peanut allergy less allergic and induce changes in their cellular and humoral immune system.

The proposed study has two primary **objectives**:

Objective #1: To treat peanut-allergic subjects with PMIT and to determine whether this protocol lowers their risk of anaphylactic reactions and causes long-term tolerance.

Objective #2: To determine the effect that PMIT has on the peanut-specific cellular and humoral response in peanut-allergic subjects.

Objective #1: To determine whether PMIT reduces peanut induced anaphylactic reactions and induces long-term tolerance in peanut-allergic subjects.

Purpose and expectations:

These studies are designed to test the feasibility and effectiveness of using PMIT to desensitize subjects with peanut allergy, and to optimize the appropriate treatment dose. We expect to demonstrate the effectiveness of PMIT by showing that subjects on PMIT will have negative double-blind placebo-controlled food challenges (DBPCFC) to peanuts following completion of a 36-month course of PMIT. We will compare the effects of high-dose PMIT (3000mg) and low-dose PMIT (300mg) against untreated controls, and we expect that PMIT will induce a significant decrease in: (a) wheal (swelling) size from a titrated skin prick test to peanut protein, (b) serum-specific IgE to peanut, and (c) adverse effects with accidental peanut ingestion. In this study we will test the hypothesis that low-dose PMIT is as successful in tolerance induction as high-dose PMIT in a young cohort of newly diagnosed subjects.

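### The SAP models IgE, IgG4 and skin test separately in each group, with no planned between-group contrast and no stated handling of early completion or withdrawal

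*SAP*

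**What the plan says.** **Protocol, Goals, Hypothesis and Objectives.** The effects of the 3000 mg and 300 mg regimens are to be set "against untreated controls, and we expect that PMIT will induce a significant decrease in" skin-test wheal size, peanut-specific IgE and reactions to accidental ingestion. One of the two primary objectives is "To determine the effect that PMIT has on the peanut-specific cellular and humoral response in peanut-allergic subjects".

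**SAP, Statistical Analysis.** IgE and IgG4 are log-transformed and skin prick test (SPT) is kept raw. "Models were fit separately for each group in R", by GEE, with functions of time as the only stated terms. Linear, quadratic and cubic curves are considered, "with the best fitting model selected for each group for each outcome selected using QIC" (QIC is the GEE analogue of AIC). The only comparison with controls that the section names is Fisher's exact test, for baseline demographics and where "categorical peanut consumption outcomes were compared between E-OIT and controls". No working correlation, weighting or missing-data rule is given.

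**SAP, Randomization.** For the primary outcome "subjects were considered a single intervention group on open label peanut OIT"; the two doses are separated for exploratory analyses. Which of these definitions applies to the immune models is not stated.

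**Protocol, Study Design and Individual Stopping Rules.** After the IgE measurement at 12 months of maintenance, a treated child with IgE no higher than 15 kU/L, a skin test no larger than 8 mm and no recent severe symptoms may be challenged early if the investigator agrees. A child who passes is finished with the study. Treated children may also leave treatment or the study after reactions, and some continue under control follow-up. Controls are seen yearly.

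**The concern.** A curve fitted to treated children alone shows how their IgE or wheal changed, not how much of the change was due to treatment. The SAP allows for natural improvement: it relies on "the 20% rate of spontaneous tolerance expected in untreated controls". That figure concerns clinical tolerance rather than IgE, but it means a flat untreated course cannot be taken for granted. If QIC picks a line in one group and a cubic in another, the groups share no coefficient to compare. Fitted values at a common time could still be compared, but the SAP names neither the time nor the comparison.

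The second problem is who remains at the late visits. Early completion depends partly on two of the modelled outcomes. An unweighted GEE generally needs data missing completely at random, and this rule departs from that by design. At stake is how the immune results are read: the objective on humoral response, and the IgE and wheal part of the first objective.

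**Working it through.** **1. The plan's own figures.** The SAP gives no number for the immune models. Its sizing is for sustained unresponsiveness (SU): 70% versus 20%, two-sided 0.05, 80% power. With pooled variance, n = [1.96·√(2·0.45·0.55) + 0.842·√(0.7·0.3 + 0.2·0.8)]² / 0.5² = (1.379 + 0.512)² / 0.25 = 14.3, so 15 per arm (power 82.0%). This reproduces the SAP, but says nothing about precision for IgE, IgG4 or SPT.

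**2. Promise against plan.**

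| Element | Protocol | SAP |
|---|---|---|
| Comparison | each dose versus untreated controls | none stated for IgE, IgG4, SPT |
| Groups | control, low, high | pooled OIT or two doses; not defined for these models |
| Time form | not addressed | chosen within each group |
| Early completion, withdrawal, move to control follow-up | all can occur | not addressed |

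**3. Why two within-group tests do not make a contrast.** Suppose two groups have the same true change and each within-group test has power p. The chance that exactly one is significant is 2p(1−p). For assumed p of 50%, 63% and 80% this is 50%, 47% and 32%.

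**4. When exit starts to depend on the outcomes.** Table 3 of the protocol has 20 increases from 6 mg (dose 7) to 3000 mg (dose 27). The 12-month-maintenance IgE therefore falls at 20 × step + 365 days: 565 for 10-day steps, 645 for 14-day steps, 785 for 21-day steps. No single calendar day is 12 months of maintenance for everyone. At day 645, a child on 21-day steps has had 645 − 420 = 225 days of maintenance, and a child on 10-day steps has been open to early challenge for 645 − 565 = 80 days.

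**5. Illustration of the exit effect (assumed inputs).** The documents give no baseline IgE, variance, slope or exit probability, so these are assumptions:
- Treated IgE on days 0, 98, 196, 280, 645, 1010 and 1375; geometric mean 20 or 40 kU/L.
- Log SDs: 1.0 (baseline), 0.25 (slope), 0.35 (residual).
- Slope −0.2 to −0.5 log per year, or a 0.3-log rise to day 280 followed by a fall.
- SPT mean 11 or 8.5 mm, SD 3, slope −0.8 mm per year.
- Eligible children complete after day 645 or 1010 with probability 0.9 × 0.4 or 0.9 × 0.7, falling with IgE in some settings. Early completion then runs from 6% to 50%.
- Withdrawal 0, 15% or 20%. The non-zero values follow the SAP's sizing ("On the basis of a prestudy assumption of 15% to 20% dropout").

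The shift is fitted end-of-follow-up treated IgE divided by the fit to the same data without exits, over linear, quadratic and cubic forms:

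| Withdrawal | Independence | Exchangeable or AR(1) |
|---|---|---|
| None | 1.11 to 1.87 | 1.03 to 1.20 |
| 15–20%, unrelated to IgE | 1.12 to 1.90 | 1.02 to 1.21 |
| 15–20%, more common at high IgE | 0.88 to 1.68 | 0.95 to 1.19 |

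For SPT the shift was −0.03 to +1.35 mm (independence) and −0.02 to +0.22 mm (exchangeable).

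At 20 per arm, with 25–27% early completion and 15% withdrawal, the end-of-follow-up OIT-versus-control difference from separate quadratic fits was off by +0.16 to +0.35 log under independence (SE about 0.35, so 0.46 to 1.0 SE). Under exchangeable correlation it was off by +0.05 to +0.10 log (SE about 0.30, so 0.17 to 0.33 SE). IgG4 was not simulated, and no run kept off-treatment data from children moved to control follow-up.

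**The case against.** The strongest reply is that the SAP is silent on a contrast rather than opposed to one. Separate fits are close to one model in which every time term interacts with group, and their estimates and standard errors can be contrasted at any common time. Within-subject change is also part of what the protocol asks: it expects decreases and frames several laboratory readouts as entry versus follow-up. The bias figures rest on inputs that are not in the documents. The large ones need an independence working correlation, which the SAP does not state. Some children who stop treatment are still followed, so not every stop is a loss of data.

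Most of this stands. Separate fitting is not itself an error, and a sponsor could keep GEE. The exit bias may be small. But silence does not supply the comparison that the protocol promises: the contrast, its time point, the group definition and the handling of exits all have to be written down. The SAP's general statements about nonparametric tests and two-sided testing do not do that.

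**Conclusion.** The gap is real and worth closing before the immune results are interpreted. As written, the SAP cannot deliver the protocol's dose-versus-control comparison for IgE and wheal size, and it plans no contrast for IgG4. This follows from the text and needs no simulation. The exit problem also follows from the protocol's rules, provided the GEE is unweighted. Its size and net direction cannot be computed from the documents and depend on the working correlation and the withdrawal pattern.

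A reader might infer three stronger things that the documents do not support:
- **That fitting by group is invalid, or that the SAP rules out a comparison.** It only fails to state one.
- **That late treated IgE will look too high, so the effect is understated.** Early completion alone pushes that way. Withdrawal at high IgE pushes back and took the shift below 1 in 13% (independence) and 16% (exchangeable or AR(1)) of the illustrative fits with that pattern.
- **That the SU endpoint or its sample size is affected.** Neither uses these models.

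**What to change.** For each outcome, fit one model to all three groups as originally assigned (control, low dose, high dose).
- **Terms:** group, time and group-by-time, with one time form per outcome shared by all groups (linear, quadratic or cubic, not chosen group by group).
- **Method:** a likelihood-based mixed model, or a GEE with a stated working correlation and weights covering both early completion and withdrawal.
- **Contrasts in change from baseline:** low dose versus control, high dose versus control, high versus low.
- **Times:** one before conditional completion can begin, around the 12-month-maintenance measurement, with a sensitivity analysis for variable build-up length; and end of follow-up, labelled sensitive to early exit.
- **Moves to control follow-up:** keep these children in their original group and say whether post-transfer data are used.
- **Status:** secondary analyses. Three outcomes × three contrasts × two times is 18 comparisons, so report estimates with intervals. Label OIT versus control as non-randomised; only high versus low is randomised.

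**Cost.** SAP wording and modest reprogramming; no new data. The result relies on the model form and on exit depending on measured history. In the illustrative runs a quadratic mixed model was within 0.94 to 1.02 of the no-exit value at end of follow-up, while a linear one ran up to 1.25 too high. Those runs placed every child's 12-month-maintenance visit at day 645. Control and SPT values are yearly, so the earlier time point needs interpolation. Intervals will be wide at 20 per arm: with an illustrative SE of 0.20 log for high versus low, exp(1.96 × 0.20) = 1.48, about 1.5-fold either way.
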